Over the past two decades there have been improved efforts to address this neglected epidemic in harder-to-treat SMI smokers (1); however, in general, advancements in cessation treatment research among SMI smokers far lags that of NMI smokers. Additionally, exciting new research results such as 1) how genetically informed biomarkers of nicotine clearance moderate smoking cessation medication treatment outcomes (7), 2) varenicline preloading increases smoking cessation rates (8), and 3) novel behavioral interventions such as ACT therapy can boost quit rates (9,10), have not been adequately tested in SMI smokers. Thus, the purpose of this proposal is to test the feasibility of whether these treatment innovations can be applied in SMI smokers with high rates of demand, practicality and acceptability for subsequent use in a large randomized clinical trial (RCT).

How Does an SMI Smoker's NMR Affect Treatment Response and Adverse Event Propensity? The NMR as measured by the ratio of 3'-hydroxycotinine (the breakdown product of cotinine) divided by the

concentration of cotinine (the breakdown product of nicotine) in a smoker's blood or urine is a genetically-informed biomarker of nicotine clearance (7). It is a surrogate measure of CYP2A6 activity - - the liver enzyme that catabolizes nicotine and other drugs and which is under genetic control11. Studies in NMI smokers have found that classifying smokers into slow versus normal nicotine metabolisers based on a cutoff score for this ratio affects how that individual is likely to respond to the 1st-line smoking cessation medications both in terms of treatment efficacy and propensity to develop side effects (7,12). The NMR predicts treatment responses to varenicline delivered at standard doses: among slow metabolisers, which represents ~40% of the general population of NMI smokers, varenicline users had comparable quit rates to nicotine patch-treated smokers and were more vulnerable to side effects than normal metabolisers. However, varenicline standard dose treatment produced higher quit rates than patch in normal metabolisers (7). To our knowledge, the NMR ratio has not been examined in a RCT of varenicline in SMI smokers. This gap is important to fill given that varenicline is the most effective monotherapy treatment for SMI smokers and these individuals have a greater propensity to develop NPSAEs.

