To gather preliminary data on the NMR, the frequency distributions of the NMR values in this SMI sample will be compared with the published data from Lerman et al. (2015) in a large sample of NMI smokers that found a cutoff score of 0.31 as the demarcating point between slow (<0.31) and normal (including rapid) metabolisers. Based on this analysis, we will calculate Cohen's d effect sizes comparing slow metabolisers on standard dose vs. normal metabolisers on low dose, as well as standard deviations and CIs, for incidence of NPSAEs of any severity to examine the direction and magnitude of the effect. Secondary outcome measures will also be examined using the same methodologies including 7-day PPA at weeks 12 and 24, to guide future studies. Regarding the secondary efficacy outcomes, and anticipating possible quit-boosting effects from ACT and varenicline preloading, we predict 7-day PPA rates at week 12 will be at least comparable to those observed in varenicline-treated EAGLES SMI participants which was 28.2%, and that 7-day PPA rates at week 24 will be at least comparable to the 20.0% observed in EAGLES (unpublished data). To examine the possible confounding effect of variable lengths of abstinence depending on when participants first attempt to quit smoking within the quit window, we will examine the effect of a time factor (i.e., the number of days from the first dose of medication to the date of the first quit attempt) with the methodologies described above.

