Consistent with recommendations on the proper sizing for pilot studies literature (50,51,53), we chose a sample size of 60 participants based on maximal accrual expectations over a 15-month recruitment period and practical cost constraints to conduct a pilot trial in this special population of smokers. Previous studies examining target sample sizes for pilot studies have argued that as few as 12 participants per group is adequate to estimate standard deviations for a two-group study (54,55), while others have suggested that a total sample of 30 is an acceptable size for a pilot study (56). With a sample of 60 (n=30 per dosing group), we will have the ability to estimate effect sizes, standard deviations, and their CIs with adequate precision to evaluate the feasibility of study procedures and to subsequently conduct formal power analyses for future RCTs (57). As such, it is amply sized as a pilot trial. For example, given a small-to-medium estimated effect of $d=0.40$, we would have 80% confidence that the true effect fell between 0.064 and 0.733 with a pilot sample of N=60. For a smaller effect of $d=0.30$, this 80% CI becomes 0.005-0.672 providing adequate precision in detecting an effect (i.e., zero not in the CI) for use in power analyses for a larger RCT. Furthermore, applying Sims' and Lewis' (2012) calculations, the sample size of N=60 will allow us to estimate standard deviations around our feasibility estimates with a minimal inflation factor (e.g., 1.09 for one-sided 80% CIs) for use in future RCT power analyses.

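### The worked precision is for 30 versus 30 dosing arms and does not carry over to the Aim 2 contrast, which is about 12 versus 18 and changes dose and NMR status together

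*Combined protocol and SAP*

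**What the plan says.** Section 9, Sample Size Determination, bases its precision on the two dosing arms: "With a sample of 60 (n=30 per dosing group), we will have the ability to estimate effect sizes, standard deviations, and their CIs". For d = 0.40 it states that "we would have 80% confidence that the true effect fell between 0.064 and 0.733 with a pilot sample of N=60". For d = 0.30 it says "this 80% CI becomes 0.005-0.672 providing adequate precision in detecting an effect (i.e., zero not in the CI". For standard deviations around the feasibility estimates it quotes a "minimal inflation factor (e.g., 1.09 for one-sided 80% CIs". It also cites literature that "as few as 12 participants per group is adequate to estimate standard deviations for a two-group study".

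The same section calls Aim 2 exploratory, says the aim proceeds by estimating effect sizes, and says the trial is not powered for clinical outcomes.

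The Data Analytic Plan for Aim 2 defines the effect size as a Cohen's d "comparing slow metabolisers on standard dose vs. normal metabolisers on low dose", for incidence of NPSAEs of any severity. Secondary outcomes, including 7-day abstinence at weeks 12 and 24, follow the same method. The only slow-metaboliser share in the document is in Section 7: "among slow metabolisers, which represents ~40% of the general population of NMI smokers". The document gives neither expected group sizes nor an interval for the Aim 2 contrast.

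**The concern.** Aim 2 rests on an estimated effect size, so precision is the sizing criterion that matters for it. The only between-group precision in the plan belongs to a different comparison. The Aim 2 contrast leaves out normal metabolisers on standard dose and slow metabolisers on low dose. A reader planning the larger trial could attach the printed interval to the Aim 2 estimate and treat it as far better determined than it is.

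There is also a problem of interpretation. Aim 2 asks whether nicotine clearance influences NPSAEs, but the two groups compared differ in both clearance and dose. The plan itself expects dose to matter: its Table 2 shows insomnia at 20.9% on the lower dose and 37.2% on the standard dose in an earlier trial. A difference in the planned contrast could therefore arise with no NMR effect at all.

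**Working it through.** **Inputs.** From Section 9: 60 participants, 1:1 allocation, 30 per arm, an 80% two-sided interval, d = 0.40 and 0.30. From Section 7: about 40% slow metabolisers, in smokers without mental illness. Applying that share here is an assumption. NMR status is not a balancing factor at randomisation, so the group sizes are left to chance.

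**Method.** The interval for d comes from inverting the noncentral t distribution with n1 + n2 - 2 degrees of freedom. As a check, the large-sample form is d ± 1.2816 × SE, with SE = √(1/n1 + 1/n2 + d²/[2(n1 + n2)]).

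**Reproducing the plan's figures (30 versus 30).**
- d = 0.40: noncentral t gives 0.064 to 0.733, an exact match. Large-sample: SE = √(0.06667 + 0.00133) = 0.261, giving 0.066 to 0.734.
- SD inflation: √(58 / 20th percentile of χ² on 58 df) = 1.09, a match.
- d = 0.30: noncentral t gives -0.034 to 0.632, not 0.005 to 0.672. The printed limits are exactly those for d = 0.34.

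**Aim 2 group sizes.** Slow on standard dose: 30 × 0.40 = 12. Normal on low dose: 30 × 0.60 = 18. If both arms have the same slow share, the two groups total 30 whatever that share is.

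**Aim 2 interval at d = 0.40.** Noncentral t at 12 versus 18 gives -0.086 to 0.879. Large-sample: SE = √(0.13889 + 0.00267) = 0.376, giving -0.082 to 0.882. The width is 0.879 + 0.086 = 0.965, against 0.733 - 0.064 = 0.669. The ratio is 1.44.

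**Range over the slow share (large-sample, d = 0.40).**

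| Slow share | Groups | 80% interval |
|---|---|---|
| 20% | 6 vs 24 | -0.189 to 0.989 |
| 30% | 9 vs 21 | -0.115 to 0.915 |
| 40% | 12 vs 18 | -0.082 to 0.882 |
| 50% | 15 vs 15 | -0.073 to 0.873 |
| 60% | 18 vs 12 | -0.082 to 0.882 |

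The 50% row is the best case (noncentral t: -0.076 to 0.869). All shares other than 40% are assumptions. Blood is not collected in the Red phase, and the number affected is not given. If 20% of NMR values were missing, 10 versus 14 would give -0.136 to 0.936.

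**Smallest observed d whose 80% interval excludes zero.** This is t(0.90, df) × √(1/n1 + 1/n2). At 30 versus 30 it is 0.33; at 12 versus 18 it is 0.49.

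**What a 2×2 analysis would give.** With 12 slow and 18 normal in each arm, the NMR comparison across both arms is 24 versus 36. At d = 0.40 the 80% interval is 0.057 to 0.739, close to the dosing-arm figure. The corner contrast gains almost nothing. Its variance factor is 1/12 + 1/18 = 0.139 with an interaction term and 0.136 without one, so the standard error falls by about 1% (√(0.136/0.139) ≈ 0.99).

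**The case against.** The strongest reply is that the plan never says the printed interval covers the NMR contrast. It names the dosing groups as its basis, ties precision to feasibility and to later power calculations, and openly calls Aim 2 exploratory and unpowered. That stands, so this is neither a failed power calculation nor an error in the d = 0.40 interval. It does not remove the gap: the aim said to work through effect sizes has no precision figure, and the general statement is easily read as covering it.

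A reader might infer several stronger things that the documents do not support.
- **That 1.09 is wrong.** It is stated for feasibility standard deviations, which use the full arms, and it is right there.
- **That the plan breaks its own 12-per-group rule.** That number is a cited benchmark, not a requirement, and the expected 12 versus 18 meets it. The chance that the slow/standard-dose group falls below 12 is 43% at a 40% share, but 84% at 30% and 10% at 50%. Only the 40% share comes from the document.
- **That the plan's zero-excluding criterion was stated for d = 0.40.** The text attaches it to d = 0.30.
- **That half the trial goes unused for NMR.** The plan also compares the whole sample's NMR distribution with published data, and says in general terms that NMR will be related to NPSAEs and cessation. It names no method for the latter.
- **That a 2×2 model would rescue the contrast's precision.** It would not. Its value is in separating the dose and NMR effects.

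The planned contrast does match Hypothesis 2 as written, so it should stay. It does not by itself answer the Aim 2 question.

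**Conclusion.** The point holds as a limit on where the stated precision applies. The interval 0.064 to 0.733 is right for the dosing arms. For the Aim 2 contrast at d = 0.40, the 80% interval is about -0.09 to 0.88, 44% wider and including zero, and an observed d of about 0.49 rather than 0.33 is needed to exclude zero. The 12 versus 18 split rests on borrowing the 40% share from smokers without mental illness. The conclusion that zero is included does not, since 15 versus 15 gives the same answer. An observed d of 0.49 or more would still exclude zero.

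Limits on the d scale are approximate here because NPSAE incidence is binary. Separately, the contrast combines dose and NMR status and cannot attribute a difference to either. The trial remains reasonable as a feasibility pilot.

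**What to change.** 1. Keep 0.064 to 0.733 and the 1.09 factor, and limit the adequate-precision statement to dosing-arm and feasibility estimates.
2. Add the Aim 2 figures beside them: about 12 versus 18, 80% interval about -0.09 to 0.88 at d = 0.40. Label the 40% share as an assumption from smokers without mental illness, and note that d-scale limits are approximate for a binary outcome.
3. Estimate the separate dose and NMR effects from a 2×2 (dose by NMR group) analysis of all 60, about 24 versus 36 for NMR. Report the planned corner contrast alongside, and say that the 2×2 analysis does not materially narrow it.
4. Correct the d = 0.30 interval to about -0.03 to 0.63 and withdraw the statement that it excludes zero; the printed limits belong to d = 0.34.

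The cost is a few sentences and one extra model, with no added participants, visits or procedures. The stated precision becomes less favourable for Aim 2 and for d = 0.30.

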9. RESEARCH DESIGN AND METHODS

Overview: This pilot trial is a Phase IV, 12-week, single center, randomized, double blind, parallel group comparison of low (0.5 mg twice daily with slower titration over one full week) versus standard dose (1.0 mg twice daily with standard titration) varenicline in SMI individuals with DSM-V BD or SSD with a 12-week, post-treatment follow-up (see Figure 3 for study design). The 16 visits after screening (Weeks 0-24) will take place using the guidelines developed by the UCSD Office of the Vice Chancellor for Research. Participants will be screened, randomized and follow the protocol according to the Research Ramp-Up phase under which the university is operating at that time of (i.e., orange, yellow, or green).

Full participation includes 14 treatment visits and 3 follow up visits. All in-person visits will take place at Pac-TARC. In addition to testing low dose varenicline in SMI smokers for the first time, three other innovative design features are incorporated to try to improve medication tolerability and short-term quit rates. 1) Plasma will be obtained at baseline to measure participants' NMR and to identify slow versus normal nicotine metabolisers. 2) A flexible quit date (between days 8-35) will be employed allowing varenicline preloading to occur prior to the TQD. 3) Ten sessions of ACT for smoking cessation will be delivered by trained counselors first in 7 in-person sessions followed by 3 sessions delivered via telephone to all participants. Randomization of participants will occur in a 1 (low dose) to 1 (standard dose) ratio and participants will be balanced on diagnosis (BD vs SSD), gender, race (White vs. non-White) and whether or not they are taking antiepileptic medications (e.g., carbamazepine) as mood stabilizers (20) which, like the demographic/ethnic factors (11,26) can influence CYP2A6 activity and affect the NMR. Volunteered, observed and solicited NPSAEs will be assessed using standardized procedures developed in EAGLES and our other prior work (4,27). However, going beyond EAGLES, we will also assess participants' tobacco withdrawal symptoms, urges to smoke, sleep disturbances, self-efficacy & confidence to quit, and satisfaction with the protocol elements. To further extend EAGLES, we will include more "real world" participants who are somewhat less psychiatrically stable and who have comorbid substance use disorders (SUDs) in early remission.

Figure 3. Study Design – ACTSLOW Pilot Trial

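### The 80% interval printed for d = 0.30 is the interval for d = 0.34; at d = 0.30 with 30 per group the interval includes zero

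*Combined protocol and SAP*

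**What the plan says.** The relevant text is in Section 9 of the combined protocol and SAP, in the paragraphs on sample size determination. After setting the total at 60 from expected accrual, cost and published pilot-size guidance, the plan states: "With a sample of 60 (n=30 per dosing group), we will have the ability to estimate effect sizes, standard deviations, and their CIs". Allocation is equal: "Randomization of participants will occur in a 1 (low dose) to 1 (standard dose) ratio".

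Two numerical illustrations follow. The first starts from "given a small-to-medium estimated effect of $d=0.40" and reports that "we would have 80% confidence that the true effect fell between 0.064 and 0.733 with a pilot sample of N=60". The next sentence carries the level and the sample size over to a second case: "smaller effect of $d=0.30$, this 80% CI becomes 0.005-0.672 providing adequate precision in detecting an effect (i.e., zero not in the CI". The plan presents this second interval as suitable for power calculations for a larger trial.

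**The concern.** The two examples share the same level, sample size and presumably method, so the second interval should sit about 0.10 lower than the first. It does not. The midpoint of the first is (0.064 + 0.733)/2 = 0.3985, close to its d of 0.40. The midpoint of the second is (0.005 + 0.672)/2 = 0.3385, well away from its stated d of 0.30. The shift between them is 0.06 where the labels imply 0.10.

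The discrepancy matters because the plan draws a conclusion from the lower limit. The printed value of 0.005 is only just above zero, and the sentence uses it to say that an observed d of 0.30 would be distinguishable from zero at 80% confidence. If the interval is misplaced by even 0.01, that conclusion fails. Supplying effect sizes and intervals for a later trial is a declared purpose of this pilot, so the smallest effect it can separate from zero should be stated correctly.

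**Working it through.** **Inputs, all from Section 9.** n1 = n2 = 30; df = 58; two-sided 80% level (10% in each tail); no allowance for dropout, since the plan's figures are given "with a pilot sample of N=60".

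**Method.** Convert d to t = d × √(n1·n2/(n1 + n2)) = d × √15 = 3.873 d. Find the noncentrality λ_L for which P(T ≥ t) = 0.10 and λ_U for which P(T ≤ t) = 0.10, with T noncentral t on 58 df. The limits for d are λ_L/√15 and λ_U/√15.

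**Step 1: reproduce the plan's first example.** At d = 0.40, t = 1.549, and the interval is 0.0640 to 0.7326. This rounds to the printed 0.064 to 0.733. The plan does not name its method, but this one matches both limits to three decimals and serves as the yardstick.

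**Step 2: apply it to the second example.**

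| d | t | 80% interval | Width | Printed for |
|---|---|---|---|---|
| 0.40 | 1.549 | 0.0640 to 0.7326 | 0.6686 | d = 0.40 (agrees) |
| 0.30 | 1.162 | -0.0341 to 0.6315 | 0.6656 | not printed |
| 0.34 | 1.317 | 0.0052 to 0.6719 | 0.6667 | d = 0.30 (as 0.005 to 0.672) |

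**Step 3: check with a second method.** The large-sample standard error at d = 0.30 is √(2/30 + 0.30²/120) = √(0.06667 + 0.00075) = 0.2596. Then 0.30 ± 1.2816 × 0.2596 = -0.033 to 0.633. Zero is inside again, so the sign of the lower limit does not depend on the method.

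**Step 4: work back from the printed limits.** Solving for the d that gives a lower limit of 0.005 yields 0.3398; solving for an upper limit of 0.672 yields 0.3401. Allowing for rounding in the third decimal (lower limit 0.0045 to 0.0055, upper limit 0.6715 to 0.6725), the two ranges are 0.3393 to 0.3403 and 0.3396 to 0.3406. They overlap only from 0.3396 to 0.3403. The limits agree with each other and point to d = 0.34.

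**Step 5: look for another reading that rescues d = 0.30.**

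| Reading at d = 0.30 | Interval |
|---|---|
| 70% level, 30 per group | 0.030 to 0.568 |
| 75% level, 30 per group | 0.000 to 0.597 |
| 80%, 38 per group | 0.003 to 0.595 |
| 80%, split 25/35 | -0.039 to 0.636 |
| 80%, split 20/40 | -0.054 to 0.652 |
| 80%, small-sample (Hedges) correction | -0.038 to 0.628 |
| 80%, one sample of 60 | 0.130 to 0.468 |

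A lower level or a larger n can lift the lower limit above zero, but the interval then becomes narrower than the printed one and the upper limit falls well short of 0.672. None of these gives the printed pair.

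**Step 6: what 30 per group does deliver.** The 80% interval excludes zero when t exceeds the 90th percentile of t on 58 df, that is, when d > 1.296 × √(2/30) = 0.335. At d = 0.30 the two-sided p-value is 0.250, so only intervals below 75.0% confidence exclude zero. At d = 0.34 the p-value is 0.193, which is below 0.20, and zero is excluded at 80%. For d = 0.30 itself to exclude zero at 80%, 38 per group (76 in total) would be needed.

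**The case against.** The strongest reply is that nothing depends on this example. The sample size comes from accrual, cost and pilot-size guidance. The Data Analytic Plan says no formal hypothesis testing is planned, and the study is described as not powered for clinical outcomes. The larger trial would be planned from effects observed in the pilot, not from a hypothetical interval in its protocol. That stands, and it makes this a wording-level correction.

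A second point is that precision means width, and the width is right: 0.666 computed against 0.667 printed. That also stands. The general claim that 60 participants allow effects to be estimated with a given precision is unaffected. What fails is the narrower claim about detection, because it depends on where the interval lies.

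Third, the method is inferred from one matching example, and a single digit could have been misread between 0.34 and 0.30 in the text extraction. The inference is strong, since both limits match to three decimals and the large-sample method agrees on the sign of the lower limit. There is no sign of a misreading, but checking the label against the source PDF is a sensible first step.

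None of these replies makes the sentence true as it reads.

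**Conclusion.** The concern holds. With 30 per group, the 80% interval for an observed d of 0.30 is about -0.03 to 0.63 and contains zero. The printed interval is the one for d = 0.34. The error is a shift of about 0.04 in location with almost no change in width, but it reverses the conclusion the sentence draws about zero. The result rests only on the plan's own inputs (30 per group, 80%, no dropout) and on the noncentral-t method that reproduces its first example; the large-sample method leads to the same conclusion. The documents do not settle whether the effect size or the interval was mistyped. The consequence is limited: the plan overstates how small an effect this pilot can separate from zero, but no design or analysis decision follows from it.

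**What to change.** First check the label against the source document. Then reconcile it with the limits in one of two ways:

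- Keep d = 0.30, print -0.03 to 0.63, and remove both the statement that zero is excluded and the claim about detecting an effect that rests on it. The sentence can still make its point about precision from the width.
- Relabel the example d = 0.34 and keep the interval and the statement about zero, both of which are then correct.

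Either change removes the contradiction. I would also add one sentence saying that with 30 per group the 80% interval excludes zero only for an observed d of about 0.335 or more, since that is what a planner of the next trial would want to know.

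The cost is one label or one pair of limits, plus a sentence. The sample size, endpoints, analysis and conduct are unaffected.

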For each feasibility measure we will compare study values to the targeted benchmarks which are based on our prior work in SMI smokers (4,49) and the relevant literature (13,19). While formal hypothesis testing is not planned given the pilot nature of this proposal (50,51), we will calculate effect sizes (i.e., Cohen's d or odds ratios [ORs]) and standard deviations, as well as confidence intervals (CI), for our feasibility variables and use

them as preliminary data for the subsequent larger RCTs. We will also calculate and examine Cohen's kappa coefficients for our clinician-obtained measures including the MINI, TLFB, C-SSRS, and assessments of NPSAEs and general AEs. These values will be used to assess the inter-rater reliability of relevant measures in SMI smokers and to refine our rater training procedures if necessary.

Aim 2: Explore whether nicotine clearance rate as measured by the NMR influences the incidence of NPSAEs in varenicline-treated SMI smokers. This exploratory aim will begin to test the **hypothesis** that incidence of NPSAEs of any severity will be higher in slow nicotine metabolisers assigned to standard dose varenicline compared with normal metabolisers treated with low dose varenicline.

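### The plan says 30 per arm estimates effect sizes precisely enough to power a later RCT, judged by an 80% CI that excludes zero; its own figures do not bear this out

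*Combined protocol and SAP*

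**What the plan says.** Section 9, Sample Size Determination, gives the design as 30 per dosing group: "With a sample of 60 (n=30 per dosing group), we will have the ability to estimate effect sizes, standard deviations, and their CIs". It says this is done "with adequate precision to evaluate the feasibility of study procedures and to subsequently conduct formal power analyses for future RCTs". Two examples follow. For d=0.40, "we would have 80% confidence that the true effect fell between 0.064 and 0.733 with a pilot sample of N=60". For d=0.30, "this 80% CI becomes 0.005-0.672", described as "providing adequate precision in detecting an effect (i.e., zero not in the CI) for use in power analyses for a larger RCT". The only allowance for pilot uncertainty is an SD inflation factor of 1.09.

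Under Aim 1 of the Data Analytic Plan: "While formal hypothesis testing is not planned given the pilot nature of this proposal (50,51), we will calculate effect sizes". These, with SDs and confidence intervals for the feasibility variables, are to serve as preliminary data for larger RCTs. Aim 2 extends effect sizes to neuropsychiatric adverse events of any severity and to 7-day point prevalence abstinence, as guidance for later studies. The Sample Size Determination text also says the pilot is not powered to test clinical outcomes.

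**The concern.** Whether an interval excludes zero says little about whether it is narrow enough to size a trial. An estimate can clear zero and still be compatible with RCT sizes that differ a hundredfold. The plan nevertheless presents zero-exclusion as evidence that the effect size is fit for a power calculation. It names no minimum important difference, no shrinkage and no conservative limit for the effect.

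Planning the next trial is a declared purpose of this pilot. A team that takes the text at its word could put an imprecise estimate into the RCT sample-size formula and run a trial well short of its nominal power.

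**Working it through.** **Inputs.** From Sample Size Determination: n=30 per arm, d=0.40 and d=0.30, the two printed 80% intervals, and the SD factor of 1.09. The documents do not give the RCT's significance level or power. I assume two-sided 5% and 80%, and show a range in step 5.

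**1. Reproduce the plan's figures.** With t = d × √(n/2) = d × √15 and 58 df, invert the noncentral t with 10% in each tail.
- d=0.40: t = 1.549, giving 0.064 to 0.733. This matches.
- SD factor: √(58 / χ²₀.₂₀(58)) = 1.090. This matches.
- d=0.30: t = 1.162, giving -0.034 to 0.632. This does not match the printed 0.005 to 0.672. A large-sample check agrees: SE = √(2/30 + 0.30²/120) = 0.260, and 0.30 ± 1.282 × 0.260 is -0.033 to 0.633. The printed limits are those of d=0.34.

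**2. When is zero excluded?** The observed d must exceed t₀.₉₀(58)/√15 = 1.296/3.873 = 0.335. The plan's second example, at 0.30, falls short. About 38 per arm would be needed.

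**3. What the d=0.40 interval means for an RCT.** Per arm, n = 2 × ((1.960 + 0.842)/d)² = 15.70/d².
- d=0.733: 15.70/0.537 = 29.2, so 30 (31 with the t correction).
- d=0.40: 15.70/0.16 = 98.1, so 99 (100 with the t correction).
- d=0.064: 15.70/0.0041 = 3,833 (3,834 with the t correction).

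The ratio of the extremes is (0.733/0.064)², about 131. In this formula it does not depend on the assumed significance level or power.

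**4. Sizing the RCT on the pilot estimate.** Simulate pilots at 30 per arm (400,000 per true d), size the RCT on the observed d by the formula in step 3, and compute its power at the true d. This assumes that the point estimate is used, which the plan does not say. The filter columns also assume that only pilots whose 80% interval lies above zero go forward.

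| True d | Pass filter | Mean d if passed | Mean RCT power, filter | Below 80%, filter | Mean RCT power, any positive d | Below 80%, any positive d |
|---|---|---|---|---|---|---|
| 0.20 | 30% | 0.51 | 23% | 100% | 58% | 64% |
| 0.30 | 45% | 0.54 | 41% | 100% | 67% | 57% |
| 0.40 | 60% | 0.57 | 56% | 84% | 71% | 53% |
| 0.50 | 74% | 0.62 | 66% | 67% | 74% | 51% |

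Over all pilots, with no filter, the mean observed d is nearly unbiased: about 0.30 for a true 0.30 and 0.405 for a true 0.40. The marked inflation comes from selection. Without selection the problem is imprecision.

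**5. Sensitivity.** With RCT significance at 5% or 10% and nominal power at 80% or 90%, filtered mean power runs 23–35% (true d 0.20), 41–55% (0.30), 56–69% (0.40) and 66–77% (0.50). Each value is below its nominal target.

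**The case against.** The strongest reply is that the zero-exclusion remark sits in a worked example about expected precision and is not a decision rule. That is correct. A reader might infer that the RCT will be sized only on effects whose interval excludes zero, or dropped by chance otherwise. No section says so, and none says that the point estimate will be used. The simulated powers are therefore conditional.

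A reader might also infer that the criterion keeps only overestimates. That is true only for a true d below about 0.335. At a true d of 0.40, about 16% of passing pilots underestimate it, and at 0.50 about 32%.

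Nor does the remark contradict the statement that no formal testing is planned, because a design-stage illustration is not a test of trial data. The phrase about being amply sized refers to a pilot trial, and N=60 was set by accrual and cost; neither is challenged here. Intervals will be reported, so later planners will see the uncertainty, and the RCT will need its own sample-size justification. The choice of 80% rather than 95% intervals is a matter of preference.

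These points limit the consequence. They do not rescue the statement itself: the precision claimed for power analyses is not there, and the d=0.30 example offered in support fails the plan's own criterion.

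**Conclusion.** The precision claim is wrong as written. Steps 1 to 3 show this without assuming any filter: the correctly printed d=0.40 interval spans about 31 to 3,830 per arm (two-sided 5% and 80% power assumed), and the correct d=0.30 interval includes zero. The plan has no safeguard on the effect size, since the 1.09 factor covers only the SD.

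An underpowered RCT is a likely result if the pilot estimate is used directly, but not a certain one. Even without selection, mean power would be about 67% to 71% for true effects of 0.30 to 0.40. The lower figures of 23% to 66% apply only if zero-exclusion were made a gate. Severity is moderate: nothing changes in this pilot's size, conduct or analysis, but a stated purpose of the pilot is misdescribed.

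**What to change.** - **Sample Size Determination:** delete the zero-exclusion criterion and the claim that effect sizes are precise enough for RCT power analyses. Correct the d=0.30 example or remove it.
- **Aim 1, Aim 2 and Sample Size Determination:** state that effect sizes are reported with confidence intervals as description only. State that the RCT target difference will be a smallest worthwhile difference, and that any pilot estimate will enter only through a conservative confidence limit.
- **Same places:** state that the pilot supplies SDs (with the 1.09 factor), pooled adverse event and quit rates, retention, adherence and accrual.

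A conservative limit reduces the risk but does not remove it. With a one-sided 80% lower limit, counting only pilots where that limit exceeds 0.05, the RCT would still miss 80% power in about 37% of cases at a true d of 0.30, against 57% when sized on any positive estimate. That is why the worthwhile difference should come first.

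The cost is a few sentences and a less favourable sample-size justification. No new data or procedures are needed.
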